1. SYNOPSIS

Name of Company: KeraNetics	Name of Product: KeraStat® Cream	Type of Study: Clinical Safety
Title of Study: Skin Prick Test of KeraStat® Cream		
Investigator(s): [name]		
Study Period: Estimated FPFV July 2019; Expected LPLVAugust 2019		
Phase of Development: Verification & Validation (Phase 3 of Design Control)		
Objective(s): 
 • To evaluate the potential for a humoral reaction to KeraStat Cream compared to a predicate device 		
Methodology: This is a within subject, open-label comparison study.		
Number of Subjects: Sufficient subjects will be screened such that approximately 20 total subjects will complete the study. Sample size for the study is not based on statistical considerations. A total of 20 subjects were deemed sufficient to assess the potential for a humoral response to KeraStat Cream compared to the predicate device in support of establishing substantial equivalence.		
Study Overview: Study Periods: The length of study participation for a subject is about 2-3 days depending on availability for the final site check. There are two skin prick site checks during the course of Day 1 with a final follow up between Days 2 and 3.		
Study Evaluations: Initial screening (Screening Visit; Visit 1) will be performed on the day of the Skin Prick Test (SPT) administration and will include obtaining demographic information, brief medical history, and abbreviated physical exam.		
On Day 1 (Visit 1) the SPT will be performed on the infrascapular region of the back to the right of the midline. Test articles will include the subject device (KeraStat Cream), predicate devices (KeraStat Gel, Biafine), positive control (histamine), and negative control (saline). Each test article will have a single administration, only the re-test will utilize a triplicate administration. The SPT will be ready for initial reading after approximately 15 minutes (but no sooner than 10 minutes and no longer than 20 minutes) following the final SPT administration in the series. When reading the test, the investigator will note the presence or absence of a wheal at all five sites and will measure the diameter of each wheal present. In order for the SPT to be valid, the wheal at the positive control site must exceed that at the negative control by 4 mm. If the above criteria are not met, the SPT will be repeated in triplicate on the infrascapular region of the back to the left of the midline, following the same protocol. Following the initial reading, the subject will remain at the testing facility.		
A second reading will be conducted approximately 6 hours (+/- 15 minutes) after SPT administration on Day 1 (Visit 1). When reading the test, the investigator will note the presence or absence of a wheal at all five sites and will measure the diameter of each wheal present. Subjects are free to leave the clinical site after the second reading. Subjects will be instructed to promptly contact the PI and go to the ER if symptoms of an allergic reaction or shock occur.		
Subjects will return to the office one to two days after initial administration for a third test reading (Visit 2). When reading the test, the investigator will note the presence or absence of a wheal in all five sites and will measure the diameter of each wheal present.		

Study: KSCM-CRD-002	Effective Date:
Version: 01	17 Jul 19

Name of Company: KeraNetics	Name of Product: KeraStat® Cream	Type of Study: Clinical Safety
Each site of test article administration will be measured for a positive reaction. A positive reaction is present when there is a measurable wheal of 3 mm or more, surrounded by a flare. Small wheals are to be confirmed by palpation. A flare alone is disregarded.		
Inclusion Criteria: Subjects must meet all of the following criteria:		

 1. Men and women, age 18-65 2. Able to understand the informed consent and provide written informed consent 3. Healthy, unmarked skin at the test area 4. Agreement to avoid consumption of antihistamines until completion of third test reading (Visit 2) 		
Exclusion Criteria: To participate in the study, subjects must not meet any of the following criteria:		

 1. Women who are pregnant, lactating/nursing or plan to become pregnant 2. Presence of skin disease, such as widespread urticaria or eczema 3. Diagnosis of infectious disease 4. Receiving corticosteroids, immunosuppressive agents, radiation or chemotherapy, topical growth factors, anxiolytics, imipramine, phenothiazine, dopamine, phenergan, clonidine, montelukast, immunotherapy, UV light therapy, H-2 antagonist, cyclosporine or any other medication the investigator feels will affect the test within the last month 5. Medical history of hypotension, severe hypertension, vasomotor instability, asthma, autoimmune disease, severe cardiac, pulmonary or renal disease 6. Tattoo in the intrascapular test area 7. History of surgical procedure/skin graft in the intrascapular test area 8. Employee or relative of employee of KeraNetics 9. Consumption of an anti-histamine within 7 days of the screening visit 10. History of hypersensitivity to histamine products 11. Any condition the investigator determines will compromise subject safety or prevent the subject from completing the study 12. Participated in an investigational study within 30 days of the screening visit 		

Study: KSCM-CRD-002 Version: 01	Effective Date: 17 Jul 19
--	--

Name of Company: KeraNetics	Name of Product: KeraStat® Cream	Type of Study: Clinical Safety
Test Product(s), Dose, and Mode of Administration:		

Subject Device: KeraStat® Cream is a non-sterile, non-implantable wound dressing intended to act as a protective covering and provide a moist environment in the management of a variety of partial thickness dermal wounds. KeraStat® Cream is provided in a screw top tube for multiple uses. Each tube contains 1 oz (29.6 mL) of KeraStat® Cream, which contains 5% keratin protein incorporated into a cream base. KeraStat Cream will be provided in its final device form and sourced by the sponsor.
 
Predicate Devices: KeraStat Gel is a sterile, non-implantable, water-based gelatinous (hydrogel) wound dressing intended to act as a protective covering in the management of a variety of partial thickness dermal wounds. It is provided in a single-use (5 mL), collapsible aluminum tube. KeraStat Gel will be provided in its final device form and sourced by the sponsor.
 
BIAFINE is a water-based emulsion formulated for the dressing and management of superficial wounds, minor abrasions, dermal ulcers, donor sites, 1st and 2nd degree burns, including sunburns, and radiation dermatitis. Biafine will be provided in its final device form and sourced by the clinical site.
 
Positive Control: Histamine will be provided as a solution of histamine base (6.0 mg/mL). Histamine will be sourced by the clinical site.
 
Negative Control: Saline (sterile) will be provided as 0.9% NaCl. Saline will be sourced by the clinical site.
		

For SPT, the infrascapular region of the back to the right of the midline will be cleaned with alcohol wipes and allowed to air dry. Five marks will be made, at least 4 cm apart, to identify the test sites. These marks will be made in a vertical line. The back will be cleaned again with alcohol wipes and allowed to air dry. A UniTest® PC (Lincoln Diagnostics, Inc) will be used, according to the instructions of use, to administer each test article. If blood is drawn, the test will be repeated for that specific site. The test will be repeated at an additional mark made along the vertical line. One minute after completing the pricks, absorbent tissue will be applied to remove residual extract, and the back will be covered with a shirt or sheet to keep the back warm. The subject will be instructed not to scratch the test area.
		

Duration of Treatment: The length of study participation for a subject is 2-3 days.
		

Concomitant Medication Restrictions: Corticosteroids, immunosuppressive agents, radiation or chemotherapy, topical growth factors, anxiolytics, imipramine, phenothiazine, dopamine, phenergan, clonidine, montelukast, immunotherapy, UV light therapy, H-2 antagonist, cyclosporine
		

Criteria for Evaluation:
 
Skin Reaction:
 
Primary
 
 Size of wheal for the subject device and predicate device at 15 minutes post SPT administration 
Secondary
 
 Size of wheal for the subject device and predicate device at 6 hours and 1-2 days post SPT administration 
Safety Parameters:
 
 Safety of the subjects will be monitored and adverse events recorded throughout the study 		

Statistical Methods: No formal statistics will be performed to compare the subject device and predicate device. Data will be summarized for each individual subject and time point. The number of subjects that meet criteria for a positive skin reaction to KeraStat Cream and/or a positive skin reaction to the predicate device(s) will be reported.
		

Safety: All subjects who participate in the study will be included in the safety analysis. Safety will be evaluated by examining the incidence and type of adverse events from the Screening Visit through study completion.
		

Study: KSCM-CRD-002 Version: 01	Effective Date: 17 Jul 19
--	--

FIGURE 1: TIME AND EVENTS SCHEDULE

Period	Skin Prick Test	
Visits	Screening Visit / Visit 1 Day 1	Follow-Up Visit/ Visit 2 (Day 2-3)
Screening		
Informed Consent	X	
Demography	X	
Brief Medical History	X	
Inclusion/Exclusion	X	
Safety Procedures		
*Vital Signs	X	
Abbreviated Physical Examination	X	
Adverse Events	X	X
Concomitant Medications	X	X
Study Treatment/General		
Skin Prick Administration	X	
Meal	X	
Assessments		
Evaluation of Response (15 min)	X	
Evaluation of Response (6 hrs)	X	
Evaluation of Response (24-48 hrs)		X

*Vital signs include height, weight, blood pressure, pulse, temperature, and respirations per minute.

Study: KSCM-CRD-002	Effective Date:
Version: 01	17 Jul 19

3. LIST OF ABBREVIATIONS AND DEFINITIONS OF TERMS

The following abbreviations and specialist terms are used in this study protocol.

Table 1: Abbreviations and Specialist Terms

Abbreviation or Specialist Term	Explanation
AE	Adverse Event
CRF	Case Report Form
CRO	Clinical Research Organization
ER	Emergency Room
EPA	Environmental Protection Agency
FDA	Food and Drug Administration
GCP	Good Clinical Practice
ICF	Informed Consent Form
ICH	International Conference on Harmonization
ICH-GCP	International Conference on Harmonization – Good Clinical Practice
IDE	Investigational Device Exemption
IEC	Institutional Ethics Committee
IRB	Institutional Review Board
KN	KeraNetics
NSR	Nonsignificant Risk
OSHA	Occupational Safety and Health Administration
PI	Principal Investigator
RIPT	Repeat Insult Patch Test
SAE	Serious Adverse Event
SPT	Skin Prick Test
SOPs	Standard Operating Procedures
SAP	Statistical Analysis Plan
USP	United States Pharmacopoeia
UV	Ultra Violet

Study: KSCM-CRD-002 Version: 01	Effective Date: 17 Jul 19
--	--

4. INTRODUCTION

4.1. Background

Active, healthy individuals are often involved in activities of daily living that put them at risk of sustaining acute skin trauma. Superficial to partial thickness abrasions may be the most common,¹ but other partial thickness injuries such as burns (450,000 burn injuries resulted in medical treatment in 2013)² and ulcers are also common. Due to the risk of untreated acute partial thickness wounds and burns becoming more serious chronic wounds or full-thickness burns, there is pressure on the medical community to find a cost-effective and efficacious wound dressing that supports healing.

KeraStat® Cream is a non-sterile, non-implantable wound dressing intended to act as a protective covering and provide a moist environment in the management of a variety of partial thickness dermal wounds. KeraStat® Cream is provided in a screw top tube for multiple uses. Each tube contains 1 oz (29.6 mL) of KeraStat® Cream, which contains 5% keratin protein incorporated into a cream base.

A biological safety profile has been established for KeraStat Cream. Biocompatibility studies were chosen and performed in accordance with ISO 10993-1:2007, “Biological Evaluation of Medical Devices Part 1: Evaluation and Testing.” Furthermore, KeraStat Cream has been subjected to a human subject Repeat Insult Patch Test (RIPT) to evaluate the irritation/sensitization potential of the medical device when applied to uncompromised skin. No adverse skin reactions were observed in 50 subjects evaluated in the RIPT study and KeraStat Cream was considered a non-primary irritant and non-primary sensitizer to the skin.

The current study is considered a nonsignificant risk (NSR) device study according to Food and Drug Administration (FDA) guidance and does not require an Investigational Device Exemption (IDE) in advance of study conduct. NSR device studies must follow the abbreviated requirements presented in 21 CFR 812.2(b) related to labeling, Institutional Review Board (IRB) approval, informed consent, monitoring, records, reports, and prohibition against promotion.

4.2. Rationale

When applied, KeraStat Cream covers the wound, isolating it from the external environment, absorbing excess exudate and facilitating a moist wound environment for the management of partial thickness wounds. KeraStat Cream contains human hair-derived keratin proteins.

Keratin, like collagen, is a structural, intermediate filament-forming protein.³ Irrespective of what species they reside in, keratin proteins are functionally important for mechanical stability and integrity and structure of the hair shaft and cells in the epithelium. These proteins are highly conserved between species, with only minor differences in expressed keratin gene sets between species. Human hair and sheep wool in particular are highly similar with equivalent keratin intermediate fibers found in each species.⁴ Keratin proteins have been used for multiple applications such as FDA cleared topical wound care products (e.g. Keratec Wound Dressings, KeraStat Gel),⁵ and multiple cosmetic and personal care applications that include hair straightening products, shampoos, conditioners, and styling agents, as well as skin care creams and ointments that are sold as cosmetics.

Study: KSCM-CRD-002	Effective Date:
Version: 01	17 Jul 19

The intended use for KeraStat Cream is as a wound dressing for management of partial thickness wounds where the normal skin barrier function has been disrupted. The keratin proteins in KeraStat Cream are derived from human hair and represent a novel component for use in a wound dressing compared to a legally marketed device (KeraStat® Gel) containing keratin proteins derived using the same manufacturing process. Animal models used for biocompatibility studies may not be fully predictive of the immune, inflammatory, and irritation responses in human subjects. While the RIPT study resulted in no observed skin reactions, the assessment is conducted on intact skin and there is a need to evaluate the potential for a humoral (B-cell mediated) immune response to KeraStat Cream on compromised skin to support its intended use. Therefore, a skin prick test is being conducted to support the continued evaluation of the safety of this product.

5. TRIAL OBJECTIVES AND PURPOSE

5.1. Objective

The objective of the present study is to evaluate the potential for a humoral reaction to KeraStat Cream compared to predicate devices.

6. INVESTIGATIONAL PLAN

6.1. Overall Study Design

This is a single site, within subject, open-label comparison study to assess the humoral reaction KeraStat Cream compared to predicate devices. The length of study participation for a subject is two to three days depending on when a subject returns for their final follow-up evaluation. The Acceptable Study Windows is shown in Table 2.

Sufficient subjects will be screened such that 20 total subjects will complete the study. We expect excellent retention throughout the duration of the study, so we will target recruitment of 22 subjects. The sample size for the study is not based on any statistical considerations. A total of 20 subjects were deemed sufficient to assess the potential for a humoral response to KeraStat Cream compared to the predicate devices in support of establishing substantial equivalence.

Initial screening (Screening Visit; Visit 1) of the subject will take place the day of the SPT administration. The Screening Visit will include collecting demographic information, a brief medical history, and an abbreviated physical exam. If a subject fulfills all the inclusion criteria, none of the exclusion criteria, and gives their informed consent they will be admitted into the study.

The SPT will be performed on Day 1 (Visit 1), after screening and consent is obtained. The test will include five agents: the subject device (KeraStat Cream), predicate devices (KeraStat Gel, Biafine), positive control (histamine), and negative control (saline). The SPT will be administered on the infrascapular region of the back to the right of the midline. The region will be cleaned with alcohol wipes and allowed to air dry. Five marks will be made using a sterile skin marker to identify the test sites. These marks will be at least 4 cm apart and made in a

Study: KSCM-CRD-002	Effective Date:
Version: 01	17 Jul 19

vertical line. Once the marks are made, the back will be cleaned again with alcohol wipes and allowed to air dry. All subjects will initially receive the agents in the same order, going in descending order from a subjects' head to feet: subject device, predicate device (KeraStat Gel), predicate device (Biafine), positive control, and negative control.

Each agent will be administered once using the UniTest® PC (Lincoln Diagnostics, Inc), following the manufacturer's instructions for use. In brief, all five agents are loaded into a well tray. A UniTest PC touch post is placed into a well, tip-down, to load an agent onto the touch post. Each well contains approximately 250-500 μ L. Allow the touch post to sit in the agent for at least 5 seconds. The touch post is removed and placed into contact at the appropriate mark for one second then pressed firmly into the skin. With proper pressure, all test sites should show a circular impression with an indented circle in the center surrounded by six dot indentations. A separate touch post is used for each agent. If blood is drawn, the test is repeated at an additional mark made along the vertical line. One minute after completing the pricks, absorbent tissue is applied to remove residual extract with care taken to avoid cross contamination of sites. When administration of the pricks is completed, the subject's shirt or a sheet will be used to cover the back and keep it warm. The subject will be instructed not to scratch the test area.

The initial evaluation of the sites will be taken after 15 (± 5) minutes following the final SPT administration in the series. When reading the test, the investigator will note the presence or absence of a wheal at all five sites and will measure the diameter of each wheal present. In order for the SPT to be valid the wheal at the positive site control must exceed that at the negative site control by 4 mm. If the above criteria are not met, the SPT will be repeated in triplicate on the infrascapular region of the back to left of the midline, following the same protocol. Three vertical lines will be made with all marks at least 4 cm apart. If the triplicate re-administration fails, the subject will be removed from the study.

Following the initial reading, the subject will remain at the testing facility. They will wait with the pricks covered by their shirt or a sheet for a period of approximately 6 hours. The subject will be instructed not to scratch the test area. During this time, the testing facility will provide a meal for the subject.

A second evaluation will be conducted 6 hours (± 15 minutes) after SPT administration on Day 1 (Visit 1). Again, the investigator will note the presence or absence of a wheal at each site and measure the diameter of each wheal present. Subjects are free to leave the clinical site after the second reading. Subjects will be instructed to not scratch or irritate the test area and to promptly contact the PI and go to the Emergency Room (ER) if symptoms of an allergic reaction or shock occur.

Subjects will return to the clinical site for a third/final test evaluation (Visit 2) one to two days after the initial test administration. When reading the test, the investigator will note the presence or absence of a wheal in all five sites and will measure the diameter of each wheal present. A subject will have completed the study after the third/final evaluation has been completed.

Study: KSCM-CRD-002 Version: 01	Effective Date: 17 Jul 19
--	--

Table 2: Acceptable Study Windows

Visit	Day Visit	Acceptable Visit Window
Screening (Visit 1)	Day -7 to Day 1	None
SPT Administration (Visit 1)	Day 1	None
First evaluation (Visit 1)	Day 1	15 minutes \pm 5 minutes after SPT administration
Second evaluation (Visit 1)	Day 1	6 hours \pm 15 minutes after SPT administration
Third/Final evaluation (Visit 2)	Day 2 – 3	1 – 2 days after SPT administration

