7.4.2. Patient Withdrawal (Premature Discontinuation from the Study)

A documented effort must be made to determine why a subject fails to return for the necessary visit or is dropped from the study, and the reason for withdrawal must be recorded in the source

Study: KSCM-CRD-002 Version: 01	Effective Date: 17 Jul 19
--	--

documents and case report form (CRF). A subject may withdraw or be removed from the study for any of the following reasons and will be treated as considered appropriate by the Investigator:

- Subject request (for any reason)
- In the opinion of the Investigator, continuation is not in the best interest of the subject.
- A serious or unexpected AE occurs such that continuation in the study is inappropriate.
- Test area (infrascapular region of the back) becomes marked or affected so that the Investigator is unable to read the test sites.
- Subject consumes antihistamines during the study.
- Pregnancy
- In the opinion of the Sponsor, continuation is not in the best interest of the subject.

If a subject is prematurely discontinued from participation in the study for any reason, the Investigator must follow up on all ongoing adverse events (if any).

In the event a subject is prematurely discontinued from the study due to an AE, or unexpected AE or serious adverse event (SAE) (as defined in Section 11.2.1), the procedures stated in Sections 11.2-11.6 must be followed.

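### A failed triplicate retest removes a subject from the study after 20 planned pricks with no later adverse event contact scheduled, yet that subject stays in the safety analysis

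*Combined protocol and SAP*

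**What the plan says.** Section 6.1 of the combined protocol and SAP gives each subject one prick per agent and reads the sites 10 to 20 minutes after the last prick. The test is valid only if the histamine wheal is larger than the saline wheal by 4 mm. If it is not, "the SPT will be repeated in triplicate on the infrascapular region of the back to left of the midline, following the same protocol". The section then adds: "If the triplicate re-administration fails, the subject will be removed from the study".

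The contacts that follow in Section 6.1 are a stay of about 6 hours, a second reading, an instruction on what to do if an allergic reaction or shock occurs, and a return visit one to two days later. On completion it says: "A subject will have completed the study after the third/final evaluation has been completed". Nothing in the section states which of these contacts apply to a removed subject.

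For safety, the Synopsis includes everyone who takes part and says: "Safety will be evaluated by examining the incidence and type of adverse events from the Screening Visit through study completion". After early discontinuation, Section 7.4.2 requires the investigator to follow adverse events that are already ongoing. A failed retest is not in that section's list of reasons for leaving. Section 7.4.3 says these subjects are not replaced. Section 12.4 puts whatever assessments a withdrawn subject completed into the summary.

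**The concern.** Failed controls make a subject's wheal results uninterpretable, but they do not undo the exposure to the test agents. Section 6.1 uses one act, removal, to settle two separate questions: whether the subject can be used in the wheal comparison, and whether safety data are still collected. The subjects concerned have had four times the planned Cream pricks of a subject whose first series was valid.

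Failure also does not show that the skin is unreactive. The criterion is a difference between two wheals, so a large saline wheal can cause failure as well as a small histamine wheal.

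What is at stake is the completeness of the adverse event summary in a study whose purpose is safety. A removed subject can remain in the denominator of the incidence with no later scheduled occasion on which an event would be recorded. The wheal comparison itself is not affected.

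**Working it through.** The plan states neither a prick count nor an observation time for removed subjects, so there is no figure of its own to reproduce.

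**1. Planned exposure.** Inputs from Section 6.1: "The test will include five agents"; "Each agent will be administered once" in the first series; a triplicate repeat, for which "Three vertical lines will be made with all marks at least 4 cm apart". Section 12.3 averages the triplicate wheals for every agent, which confirms that all five are repeated.

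- First series: 5 × 1 = 5 pricks, 1 of Cream.
- Retest: 5 × 3 = 15 pricks, 3 of Cream.
- Total after a retest: 5 + 15 = 20 pricks, 1 + 3 = 4 of Cream. The ratio is 20/5 = 4 overall and 4/1 = 4 for Cream.

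Sites that bleed are pricked again, so 20 is the planned count and not a maximum.

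**2. Scheduled contacts, following Section 6.1 and Figure 1 as written.**

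| Subject | Planned pricks (Cream) | 15-minute reading | 6-hour reading | Visit 2 reading and adverse event query |
|---|---|---|---|---|
| First series valid | 5 (1) | yes | yes | yes |
| Retest passed | 20 (4) | yes, both series | yes | yes |
| Retest failed | 20 (4) | yes, both series | none stated after removal | none stated after removal |

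The second and third rows have equal exposure. The gap follows from failing the retest, not from the number of pricks.

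**3. Routes by which a later event could be recorded.** Sections 11.2.2 and 11.4.1 elicit adverse events at visits, and Figure 1 places these at Visits 1 and 2. Section 11.2 ends detection when study-related procedures are complete, and a removed subject has none left. Sections 7.4.2 and 11.6 follow events already reported or ongoing. Section 11.2.2 encourages spontaneous reports, and Section 11.5.3 covers emergencies. None of these schedules a search for an event that starts after removal.

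**4. Possible effect on incidence.** Assume N participants, m removed, the same chance q of a later-onset event in everyone, and no spontaneous report from removed subjects. With all N in the denominator, the expected recorded incidence is q × (N − m)/N. Taking N = 22 (the recruitment target in Sections 6.1 and 12.2):

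- m = 1: 21/22 = 0.955, so about 5% of the later-onset incidence is lost.
- m = 2: 20/22 = 0.909, so about 9% is lost.

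The loss would be larger if more pricks raise q, and smaller if removed subjects report events themselves. The values of m are assumptions.

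**5. Chance that the rule is used at all.** No retest failure rate is given. With an assumed rate p per subject, the chance of at least one failure among 22 is 1 − (1 − p)^22:

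- p = 1%: 1 − 0.99^22 = 0.198
- p = 5%: 1 − 0.95^22 = 0.676
- p = 10%: 1 − 0.90^22 = 0.902

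**6. Time scale, if removal happens at the retest reading.** That reading comes 10 to 20 minutes after the last retest prick. The 6-hour reading has a window of 345 to 375 minutes. The ratio runs from 345/20 = 17 to 375/10 = 38. The timing of removal is inferred, so this is an illustration only.

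**The case against.** The strongest reply is that the text leaves follow-up unclear and does not clearly end it. Section 6.1 gives no time of removal or departure. Its next paragraph has the subject stay at the facility after the initial reading and makes no exception, and the Synopsis has the same stay with no removal rule at all. A reader might infer that removed subjects leave within minutes; the documents do not say so. What stands is that the stay is not expressly extended to removed subjects either, and that even a full stay would leave Visit 2 unscheduled for them.

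Safeguards also exist. Section 7.4.2 leaves the management of subjects who leave to the investigator's judgment, and the reporting routes in step 3 remain open. It would be wrong to say that late reactions cannot be observed. The instruction about allergic symptoms is addressed to subjects generally, and the consent pages are not available here, so it cannot be called missing.

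Three further readings go too far:

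- That the most heavily exposed subjects have the shortest follow-up. Subjects who pass the retest have the same 20 pricks and every reading.
- That removed subjects will be counted as free of adverse events. No such rule is written; Section 12.4 speaks only of completed assessments. Understatement is a risk, not a planned analysis.
- That observation is 72 to 288 times shorter (1440/20 to 2880/10 minutes). This sets a reading interval against the time to Visit 2, for most of which continuing subjects are also away from the site.

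Frequency is also a fair objection. The rule needs two control failures in subjects already screened for antihistamines and other listed drugs, so it may never be used.

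**Conclusion.** The point holds for failed retests only. Followed as written, Section 6.1 removes a subject with 20 planned pricks (4 Cream) and leaves no later scheduled adverse event contact, while the Synopsis keeps that subject in a safety analysis running to a completion point that the subject cannot reach. Later-onset events are not actively sought in these subjects, and the adverse event incidence could be understated.

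The size cannot be fixed from the documents. One such subject is 1/22 to 1/20, about 5% of the study. At assumed failure rates of 1% to 10%, the chance of at least one is about 20% to 90%. The conclusion rests on reading removal as the end of scheduled contacts, which no section contradicts for Visit 2 but which is open for the on-site stay. The change is worth making because it is cheap, but the study does not fail without it.

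**What to change.** 1. In Sections 6.1 and 7.4.2, make a failed retest a reason for being non-evaluable for the wheal comparison and not a reason for ending safety data collection. Adverse event collection then continues through the already scheduled Visit 2 contact.
2. Reconcile Sections 6.1, 7.4.2 and 11.2, and the Synopsis, on which on-site observation and which instructions apply after a failed retest. The clinical content is for the sponsor and the investigator to settle.
3. State from which series the 6-hour time is counted once a retest has been given. Section 6.1 and Table 2 refer only to the administration, and a retested subject has two. This matters for passed retests as well.
4. In the safety summary, report how many subjects were assessed for adverse events at each contact, so that a missing contact is visible and is not read as no event.

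The cost is protocol wording, one extra line of counts in the summary, and keeping a few non-evaluable subjects until Visit 2. No new visit is needed.
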